## ABBREVIATIONS AND DEFINITIONS OF TERMS

UTHSC	University of Tennessee Health Science Center
IMPACT	Integrated Modular Patient-Reported Outcome Assessment for Craniomaxillofacial Trauma
IMPACT-G	General Module of the IMPACT
IMPACT-N	Nasal Module of the IMPACT
IMPACT-O	Orbital Module of the IMPACT
IMPACT-J	Jaw Module of the IMPACT
PRO	Patient-Reported Outcome
PROM	Patient-Reported Outcome Measure
QOL	Quality of Life
IRT	Item Response Theory
MCID	Minimally Clinically Important Difference
IRB	Institutional Review Board
MMF	Maxillomandibular Fixation

## ABSTRACT

**Context:** Maxillofacial trauma literature is dominated by objective, physician-rated outcomes, leaving a gap in our understanding of the patient experience.

**Objectives:** The primary objective of this study is to validate a novel patient-reported outcome Measure (PROM) for maxillofacial trauma: Integrated Modular Patient-Reported Outcome Assessment for Craniomaxillofacial Trauma (IMPACT).

**Study Design:** Prospective, multi-institutional survey study.

**Setting/Participants:** Patients presenting for routine clinic follow-up for maxillofacial trauma at high-volume trauma centers throughout the United States will be screened. Adults with fractures of the upper face, midface, mandible, and/or facial soft tissue injury within the last 12 months will be included.

**Study Procedures, Interventions and Measures:** Participants providing informed consent will complete the appropriate IMPACT survey modules based on their fracture pattern: IMPACT-N for involvement of the nasal region, IMPACT-O for the orbital region, and/or the IMPACT-J for the jaw. Patients will also complete the 15 Dimension (15D) QOL survey as a control. Surveys will be collected at two consecutive appointments. Independent variables related to the trauma will be abstracted for analysis.

**Main study outcome measures:** The primary objective will be to determine criterion validity of each IMPACT module and subscale via correlation with the 15D (Pearson's r). Secondarily, we will analyze internal validity and reliability (via Cronbach alpha and Item Response Theory [IRT] analysis). Consecutive surveys will be compared for reliability. The minimally clinically important difference (MCID) will be calculated using an anchor-based approach. Finally, IMPACT scores will be analyzed across independent variables including sociodemographic variables, trauma details, and management approach.

---

---

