## 1 BACKGROUND INFORMATION AND RATIONALE

### 1.1 Introduction

Maxillofacial trauma literature is dominated by objective and physician-rated outcomes, leaving a paucity of patient-reported outcome (PRO) research. In fact, no PRO measure (PROM) has ever been validated in this population, posing a tremendous barrier to our understanding of the patient experience. This project will overcome this barrier by validating a novel PROM: The Integrated Modular Patient-Reported Outcome Assessment for Craniomaxillofacial Trauma (IMPACT). Integrating the IMPACT into future studies may revolutionize the field by providing novel evidence for controversial topics such as maxillomandibular fixation techniques, surgical approaches, adjunctive therapies, and more.

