### 1.2 Relevant Literature and Data

A paucity of patient-reported outcome (PRO) research in the field was first exposed by a brief literature review from the United Kingdom in 2019. More recently, the host institution for this study performed a comprehensive, scoping review of all PRO studies in maxillofacial trauma across some of the largest academic databases between 1999 and 2024, identifying only 88 publications over that 25-year period (data unde review). PRO measures (PROMs) that have been used are heterogenous and not designed for or validated in maxillofacial trauma patients. Most of them focus on psychosocial outcomes and the Hospital Anxiety and Depression Scale (HADS) has been used most frequently. The scarce PRO data we do have repeatedly demonstrates that maxillofacial trauma patients suffer increased rates of mental health disease. Feelings of anxiety or depression are driven by unique aspects of each patient's trauma experience, aspects that cannot be understood from imaging or chart review. Unfortunately, there is no validated instrument to study this experience, posing a barrier to our understanding and management of mental health disease in these patients.

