### 5.1.2 15D Survey

The 15D is a well-established survey to assess QOL over numerous medical and/or surgical patients. It has 15 questions each on unique 5-point Likert scale and all related to some QOL theme. This survey has previously been used in maxillofacial trauma. It was chosen as a control for this study given its robust validity for measuring QOL and several individual themes that are specifically related to maxillofacial trauma such as eating, drinking, speech, anxiety, and depression.

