#### 6.4.1 Baseline Data

The following chart review variables will be abstracted after informed consent is obtained and the initial survey is completed. This data will be summarized descriptively with average, median, range, interquartile range, and standard deviation, as appropriate. Each variable will then be tested for association with IMPACT scores on univariable analysis. Clinically or statistically significant variables will then be included in subsequent multivariable testing.

---

---

- Sociodemographic data: Age, sex, race, ethnicity, marital status, smoking status, payor type (private, medicare, Medicaid, government, none / self-pay, or other), and Social vulnerability index (SVI) values based on home address.
  - SVI: A measure of social vulnerability assigned to each zip code or census tract by the Center for Disease Control and Prevention.
- Trauma data: Mechanism, concomitant multisystem trauma, airway status, level of care (discharged from emergencet room, floor/stepdown admit, intensive care admit), presenting signs or symptoms (cranial nerve weakness, trismus, malocclusion, visual impairment), description of facial trauma, comprehensive facial injury (CFI) score, and Facial Injury Severity Score (FISS).
  - CFI: An objective scale based on maxillofacial imaging and clinical exam providing an integer that represents fracture severity by correlating it with the operative time for repairing each fracture.
  - FISS: An objective scale based on maxillofacial imaging and clinical exam providing an interger that represents the objective severity of facial trauma by correlation with the cost of management.
- Management data: Treatment (observation, bedside intervention, or surgical repair), type of surgical repair (closed reduction, open reduction, internal fixation, external fixation, and maxillomandibular fixation [MMF]), hospital length of stay (days), disposition (home versus medical facility)
- Objective complications: Wound infection or dehiscence, Malunion or nonunion, hardware extrusion, or any unplanned return to the emergency department, admission or reoperation related to the facial injury.
- Survey metadata: time from trauma to survey (days), time from intervention to survey (if applicable; days), presence of maxillomandibular fixation at the time of the survey.

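### Correlation with the 15D is convergent, not criterion, validity, and cannot by itself justify calling a regional module or subscale valid

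*Protocol*

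**What the plan says.** The abstract gives the primary objective as to "determine criterion validity of each IMPACT module and subscale via correlation with the 15D". Sections 2.1 and 6.1 speak more generally of validity for measuring QOL. Section 6.4.3 sets the rule: a module or subscale counts as valid if its Pearson correlation with the 15D is significant at 0.05 and exceeds 0.4. The rule covers all four modules and all their subscales, including Orbital Function and Nasal Appearance (Section 5.1.1).

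On the standing of the comparator, Section 1.1 states that "no PRO measure (PROM) has ever been validated in this population". Section 1.2 adds that "PRO measures (PROMs) that have been used are heterogenous and not designed for or validated in maxillofacial trauma patients". Section 5.1.2 describes the 15D in general terms ("The 15D is a well-established survey to assess QOL over numerous medical and/or surgical patients"), notes that "This survey has previously been used in maxillofacial trauma", and justifies it as follows: "It was chosen as a control for this study given its robust validity for measuring QOL and several individual themes". The themes it lists are eating, drinking, speech, anxiety and depression.

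Section 6.4.1 also abstracts "presenting signs or symptoms (cranial nerve weakness, trismus, malocclusion, visual impairment". Under Sections 6.1, 6.4.3 and 6.4.4, variables that predict IMPACT scores are controlled for in a multivariable model. Cronbach alpha, IRT and the predictor analyses are secondary and do not enter the rule.

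**The concern.** Criterion validity means agreement with a measure accepted as the standard for the construct in the population studied. If no such standard exists, correlation with an established generic instrument is convergent evidence, one strand of construct validity. The abstract therefore names a stronger property than the analysis can show.

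The label matters because the same correlation is the whole verdict. The 15D is a general QOL score with anxiety and depression among its themes, and Section 1.2 reports raised rates of mental health disease in these patients. Shared distress is thus a plausible source of correlation for any module. A regional score that mostly reflected distress could be declared valid, and the rule would not distinguish it from one that measures orbital, nasal or jaw problems. Section 1.1 expects the instrument to inform questions such as fixation techniques and surgical approaches, where that distinction counts.

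**Working it through.** **Step 1: the plan's own figures.** Section 6.5 gives 150 patients per module, a 30% share for IMPACT-O and 33% nonresponse. 150 / 0.30 = 500 recruited, as stated. 500 / (1 − 0.33) = 747 invited, against 750 stated. Both reproduce. The protocol gives no power calculation for the correlation, so there is none to check.

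**Step 2: which half of the rule binds.** At n = 150, two-sided 5% (sidedness is not stated), the critical correlation is t / √(n − 2 + t²) with t = 1.976, that is 1.976 / √(148 + 3.905) = 0.160. Any r above 0.4 is therefore significant, and r > 0.4 alone decides. An observed r of 0.40 has a 95% CI of 0.26 to 0.53 by Fisher z and shares 0.4² = 16% of variance.

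**Step 3: a module with no regional content.** Assume that the module and the 15D correlate only because both load on general distress. Both are oriented so that higher is worse. The expected r is the product of the loadings, and P(pass) = 1 − Φ[(atanh 0.4 − atanh r) × √147], with atanh 0.4 = 0.4236 and √147 = 12.124. The loadings are assumptions.

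| Module loading | 15D loading | True r | atanh r | z | P(observed r > 0.4) |
|---|---|---|---|---|---|
| 0.60 | 0.65 | 0.390 | 0.4118 | 0.14 | 44% |
| 0.65 | 0.70 | 0.455 | 0.4910 | −0.82 | 79% |
| 0.70 | 0.70 | 0.490 | 0.5361 | −1.36 | 91% |

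A simulation (20,000 samples of 150 per setting) over a wider grid, with 15D loadings of 0.5 to 0.8 and module loadings of 0.6 to 0.9, gives a true r of 0.30 to 0.72 and pass rates of 8% to 100%. At 0.7 and 0.7 it gives 92%, in line with the table.

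**Step 4: the opposite case.** A module that loads 0.9 on regional function and not on distress, with the 15D loading 0.1 to 0.4 on that function, has a true r of 0.09 to 0.36 and passes 0% to 29% of the time. The rule can therefore also fail a good regional score.

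**Step 5: sample size by module.** At 500 recruited, IMPACT-N and IMPACT-J would have about 500 × 0.40 = 200 and 500 × 0.60 = 300 patients. Larger n moves each pass probability further from 50%. It does not change what the rule measures.

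**Step 6: the label.** Section 1.1 says that no PROM is validated in this population. Section 1.2 says the same of the PROMs used so far. Section 5.1.2 places the 15D among those used and claims validity for QOL in general. On these premises the 15D is a comparator.

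**The case against.** The best reply is that the objective, the endpoint and the rule all concern validity for measuring QOL, and that correlation with an established QOL score is direct evidence of that. Section 5.1.2 defends the choice ("It was chosen as a control for this study given its robust validity for measuring QOL"), and *criterion* appears only in the abstract. This stands in part: the 15D correlation is relevant and should stay, and the labelling error is confined to one place. It does not make the 15D a reference standard, and it does not support an unqualified verdict for subscales such as Nasal Appearance, which are narrower than general QOL.

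Three stronger readings are tempting, and the protocol does not support them.

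- *The protocol says that the 15D is unvalidated here.* It never says so of the 15D by name. This is an inference from Sections 1.1, 1.2 and 5.1.2 together.
- *The chart signs play no part in the primary analysis.* They can enter it as covariates under Sections 6.1, 6.4.3 and 6.4.4. What they lack is a role as a test of specificity. Section 6.4.1 lists no direct measure of distress, so adjustment is not designed to remove it, though it may remove some. The calculations above use the unadjusted r.
- *A score should be called valid only if it also separates patients with and without a presenting sign.* A plain contrast cannot separate regional content from distress if patients with the sign are also more distressed. The signs listed include no clear nasal one, and the IMPACT-G and Appearance scores would have no evident route to a positive verdict.

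Hypotheses on known groups or divergent validity may also sit in an analysis plan that is not shown, so their absence is not the point. The point is the wording that the protocol fixes.

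**Conclusion.** The point holds in a limited form. On the protocol's own premises, the primary analysis yields convergent validity evidence, and the abstract's criterion claim is unsupported. Because r > 0.4 with one generic score is the only effective condition in Section 6.4.3, a regional module or subscale *can* be declared valid through shared distress alone. A reader might infer that such a score *will* be declared valid, but that depends on loadings the protocol does not give: 44% to 91% in the illustrative cases, and 8% to 100% over the wider grid. These figures assume a single shared distress factor, n = 150, no adjustment, and both scores oriented in the same direction. The label and the scope of the verdict do not depend on these assumptions.

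**What to change.** 1. In the abstract, replace *criterion validity* with *convergent validity*.
2. In Section 6.4.3, replace the verdict of valid with *convergent validity with general QOL (15D) supported*, and state that no regional module or subscale will be called valid without qualification from this test alone.
3. If regional specificity is examined with data already collected, report it as supporting evidence that does not change the verdict. Make it a divergent comparison, for example whether a presenting sign relates more strongly to the matching Function subscale than to Psychosocial Function.

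Items 1 and 2 cost only wording. Item 3 needs a few prespecified comparisons and no new patients, surveys or visits. Presenting signs may have resolved in surveys late in the 12-month window, which would weaken these comparisons. The main downside is a more modest headline claim.

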## 1 BACKGROUND INFORMATION AND RATIONALE

### 1.1 Introduction

Maxillofacial trauma literature is dominated by objective and physician-rated outcomes, leaving a paucity of patient-reported outcome (PRO) research. In fact, no PRO measure (PROM) has ever been validated in this population, posing a tremendous barrier to our understanding of the patient experience. This project will overcome this barrier by validating a novel PROM: The Integrated Modular Patient-Reported Outcome Assessment for Craniomaxillofacial Trauma (IMPACT). Integrating the IMPACT into future studies may revolutionize the field by providing novel evidence for controversial topics such as maxillomandibular fixation techniques, surgical approaches, adjunctive therapies, and more.

### 1.2 Relevant Literature and Data

A paucity of patient-reported outcome (PRO) research in the field was first exposed by a brief literature review from the United Kingdom in 2019. More recently, the host institution for this study performed a comprehensive, scoping review of all PRO studies in maxillofacial trauma across some of the largest academic databases between 1999 and 2024, identifying only 88 publications over that 25-year period (data unde review). PRO measures (PROMs) that have been used are heterogenous and not designed for or validated in maxillofacial trauma patients. Most of them focus on psychosocial outcomes and the Hospital Anxiety and Depression Scale (HADS) has been used most frequently. The scarce PRO data we do have repeatedly demonstrates that maxillofacial trauma patients suffer increased rates of mental health disease. Feelings of anxiety or depression are driven by unique aspects of each patient's trauma experience, aspects that cannot be understood from imaging or chart review. Unfortunately, there is no validated instrument to study this experience, posing a barrier to our understanding and management of mental health disease in these patients.

### 1.3 Compliance Statement

This study will be conducted in full accordance with the institutional review board (IRB) for each participating institution. Each institution will obtain full, independent approval to perform this study from their home IRB. As the host institution, The University of Tennessee Health Science Center (UTHSC) Policies and Procedures and all applicable Federal and state laws and regulations will be followed. All episodes of noncompliance will be reported. Collection, recording, and reporting of data will be accurate and will ensure the privacy, health, and welfare of research subjects during and after the study.

---

---

## **2 STUDY OBJECTIVES**

### **2.1 Primary Objective**

The primary objective of this study is to determine the validity of each IMPACT module and subscale for measuring QOL in patients with maxillofacial trauma.

### **2.2 Secondary Objectives**

1. Analyze IMPACT module and subscale scores across baseline sociodemographic, injury, and treatment variables in order to understand which factors influence QOL.
2. Analyze the reliability of each IMPACT module and subscales.
3. Determine the sensitivity to change for IMPACT modules and subscales.
4. Calculate the minimally clinically important difference (MCID) for each IMPACT module and subscales.

---

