### **4.1 Observational Period**

All patients presenting to clinic for maxillofacial trauma will be screened using the inclusion and exclusion criteria above. Patients who satisfy these criteria will be asked to complete surveys at two consecutive appointments during any of their regular clinical follow-up for maxillofacial trauma within one year from the injury.

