#### **4.1.1 Procedures: Initial Visit**

Informed Consent: Patients will be introduced to the study and asked to complete informed consent. Those who do not wish to participate will not be given the surveys and will undergo the routine clinical care as otherwise scheduled.

IMPACT and 15D Survey Completion: A member of the research team will assign and administer the appropriate IMPACT modules for each patient based their fracture pattern (preferably on a tablet, but may complete on paper if needed). All patients will also complete the 15D QOL survey at each visit.

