#### **4.1.2 Procedures: Follow-up Visit**

IMPACT and 15D Survey Completion: A member of the research team will assign and administer the appropriate IMPACT modules for each patient based their fracture pattern (preferably on a tablet, but may complete on paper if needed). Alternatively, patients will be

---

offered the opportunity to provide their email address to complete the follow-up survey at home at a later date.

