### 6.2 Secondary Endpoints

1. Identification of independent predictors of IMPACT scores including baseline sociodemographic, injury, and treatment variables.
2. Determine the reliability of IMPACT scores.
3. Calculate the change in IMPACT scores at subsequent clinic visit(s).
4. Calculate the MCID for each IMPACT module and subscale.

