#### 6.4.3 Analysis of Primary Outcome of Interest

This validity of the IMPACT in measuring QOL will be determined by calculating Pearson's r between the score from each IMPACT module and subscale with the 15D QOL survey.

---

---

Each module or subscale will be considered valid if it shows significant ( $p < 0.05$ ) and at least moderately-positive correlation ( $r > 0.4$ ) with the 15D. All independent variables that influence IMPACT scores will be controlled for in a multivariable regression model.

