#### **6.4.4 Analysis of Secondary Outcomes of Interest**

1. IMPACT independent predictors: This secondary objective will identify independent variables that are associated with IMPACT scores. Multivariable logistic and linear regression models will be developed for categorical and continuous independent variables, respectively, and tested for association with each IMPACT score. Those independently associated with the IMPACT will be reported and factored into the multivariable regression for the primary endpoint.
2. Internal consistency and reliability will be measured by Cronbach alpha testing, item-response theory (IRT), and correlation between initial and followup surveys for patients completing both within one month.
3. The MCID for each module and subscale will be calculated using an anchor-based approach with a single item that addresses each patient's overall satisfaction.

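### Sensitivity to change is a secondary objective, but its endpoint is only the change in IMPACT scores, with no external criterion of change and no analysis in 6.4.4

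*Protocol*

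**What the plan says.** Section 2.2 of the protocol lists four secondary objectives. The third is to "Determine the sensitivity to change for IMPACT modules and subscales". Section 6.2 lists four endpoints that match these objectives, and the third reads "Calculate the change in IMPACT scores at subsequent clinic visit(s". It names no comparator, anchor or expected result.

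Section 6.4.4 has three numbered analyses: predictors, internal consistency and reliability, and the MCID. Paired surveys appear there only as a reliability measure, the "correlation between initial and followup surveys for patients completing both within one month". The abstract likewise compares consecutive surveys for reliability. One external anchor is named, and it is assigned to the MCID: "The MCID for each module and subscale will be calculated using an anchor-based approach with a single item that addresses each patient's overall satisfaction".

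On data collection, section 4.1 has patients "asked to complete surveys at two consecutive appointments during any of their regular clinical follow-up". Section 4.1.1 states "All patients will also complete the 15D QOL survey at each visit". The follow-up procedure in 4.1.2 opens "IMPACT and 15D Survey Completion: A member of the research team will assign and administer the appropriate IMPACT modules for each patient". It then allows the follow-up survey to be completed at home by email, without listing what that version contains. In the analysis the 15D is used for score against score: 6.4.3 speaks of "calculating Pearson's r between the score from each IMPACT module and subscale with the 15D QOL survey".

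**The concern.** Sensitivity to change means that scores move when the patient's condition moves. Showing it needs some indication, from outside the instrument, of who changed and in which direction. IMPACT change on its own cannot be interpreted. No change may mean stable patients or an insensitive scale, and a change may be real recovery or an effect of answering a second time.

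The design sharpens this. Patients may enter at any time up to 12 months after injury (3.3.1), and the two surveys fall at whichever routine appointments come next, so true change will differ widely between patients. Pairs completed within one month also serve the reliability analysis. Without a criterion, the same within-patient difference could be read as unreliability under objective 2 and as sensitivity under objective 3.

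The risk is that an unanchored change is published as evidence of responsiveness, or that a small change is taken as a failure of the scale. The missing method in 6.4.4 could by itself be left to a statistical analysis plan. The endpoint could not: the protocol fixes it, and a plan that followed it literally would inherit the gap.

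**Working it through.** **1. The plan's own figures.** The protocol gives no figure for sensitivity to change. Its sample size (6.5) is driven by IMPACT-O:
- Enrolment: 150 / 0.30 = 500, as stated.
- Invitations: 500 / (1 − 0.33) = 746.3, so 747; with one third, 500 / (2/3) = 750, as stated.

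This arithmetic is sound. It caps the expected pairs for IMPACT-O at 500 × 0.30 = 150, reached only if everyone returns the second survey. Section 6.5 projects no loss between the two surveys.

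**2. Objectives, endpoints and analyses side by side.**

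| Topic | 2.2 | 6.2 | 6.4.4 |
|---|---|---|---|
| Predictors | objective 1 | endpoint 1 | item 1 |
| Reliability | objective 2 | endpoint 2 | item 2 |
| Sensitivity to change | objective 3 | endpoint 3: IMPACT change only | none |
| MCID | objective 4 | endpoint 4 | item 3 |

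**3. Can IMPACT change alone separate a responsive scale from an unresponsive one?** A simulation used 150 pairs and 4,000 runs. 15D change was standard normal, and IMPACT change = μ + ρ × (15D change) + √(1 − ρ²) × noise, so its SD is 1. The correlation ρ stands in for responsiveness. The standardised response mean (SRM) is mean change divided by the SD of change.

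| μ (SD units) | ρ | SRM | Runs with mean change significant | Mean change–change r |
|---|---|---|---|---|
| 0.5 | 0 | 0.50 | about 100% | 0.00 |
| 0.5 | 0.3 | 0.50 | 100% | 0.30 |
| 0.5 | 0.6 | 0.50 | 100% | 0.60 |
| 0 | 0 | 0.00 | about 5% | 0.00 |
| 0 | 0.3 | 0.00 | about 5% | 0.30 |
| 0 | 0.6 | 0.00 | about 5% | 0.60 |

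The SRM and the test of mean change follow μ and ignore ρ. Only the correlation of the two changes recovers ρ. A hand example shows the same: if half the patients improve by 10 points and half worsen by 10, a perfectly responsive scale has mean change 0.5 × 10 − 0.5 × 10 = 0.

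**4. Precision of the remedy.** The 95% CI is tanh(atanh(r) ± 1.96/√(n − 3)). Power against zero is Φ(atanh(r) × √(n − 3) − 1.96). With r = 0.40 in absolute value (illustrative), atanh(r) = 0.4236. For n = 75, 1.96/√72 = 0.2310, so the limits are tanh(0.1927) = 0.19 and tanh(0.6546) = 0.57.

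| Pairs (assumed) | 95% CI for r = 0.40 | Power against r = 0 |
|---|---|---|
| 150 | 0.26–0.53 | above 99% |
| 100 | 0.22–0.55 | 99% |
| 75 | 0.19–0.57 | 95% |
| 45 | 0.12–0.62 | 78% |

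The last row is 30% of 150 and shows when precision becomes poor.

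**The case against.** The strongest reply is that the endpoint is underspecified and not wrong. Section 6.2 does not say mean change, does not say that change is tested against zero, and does not rule out comparison with an external measure. Individual change scores are the raw material of any responsiveness analysis, including the one proposed here. That stands. A reader might infer that the objective cannot be answered from this study, but the documents do not support this: the planned data allow an answer, and what is missing is the step that turns change scores into evidence. The simulation and the ±10 example refute only a mean or standardised mean change.

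Other provisions help in part:
- Section 6.4 promises effect sizes with 95% CIs. A standardised change could be reported under it, but it would still rest on IMPACT alone.
- Time from trauma, time from intervention and fixation status at the survey are recorded (6.4.1). They help to show where recovery is expected, but do not show who recovered.
- The satisfaction item could serve as a criterion. A reader might infer that the 15D is the only remedy; it is not. However, 6.4.4 ties the satisfaction item to the MCID and does not say that it is applied to change.

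The 15D also has limits. Four of the ten subscales concern appearance (5.1.1), while the trauma-related 15D themes named in 5.1.2 are eating, drinking, speech, anxiety and depression. An appearance subscale could track real change and still correlate weakly with the 15D. Grouping patients by 15D change needs a cut-off that the protocol does not give, and 75 pairs split three ways average 25 per group. It would therefore be wrong to infer that the remedy has no downside.

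**Conclusion.** The point holds as a mismatch between an objective and its endpoint. Objective 3 asks for sensitivity to change, endpoint 3 supplies only IMPACT change, and no stated analysis links the two. The primary endpoint and the sample size are untouched, so it is worth correcting but does not threaten the study.

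The protocol shows no numerical loss. The simulation demonstrates the logic and does not estimate harm, and it takes correlation with 15D change as a stand-in for responsiveness. The intervals assume r = 0.40 and 75 to 150 pairs, and the protocol gives neither. That the 15D is available at both surveys rests on 4.1.1 and the label in 4.1.2. Neither section says outright that the emailed version includes it.

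**What to change.** Keep the change score as endpoint 3, and make these additions:

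1. In 6.2 and as a new item in 6.4.4: the correlation between change in each IMPACT module and subscale score and change in the 15D over the two surveys, with 95% CI.
2. Fix in advance the expected direction and minimum size. The direction must allow for higher IMPACT scores meaning worse quality of life (6.4.2) and for the direction of the 15D score, which the protocol should state. Set lower expectations for the four appearance subscales. The satisfaction item may be a supporting anchor.
3. State which survey pairs are used, since those within one month serve the reliability analysis. If pairs are restricted, report how many remain.
4. State in 4.1.2 that the follow-up survey, including the emailed version, contains the 15D.
5. Optionally, give standardised response means by 15D change group, descriptively and with the cut-off stated.

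The cost is wording and a little extra analysis. No further data collection is needed if the follow-up survey contains the 15D as 4.1.1 implies, and the sample size need not change unless paired completion is very low. Because the 15D is an imperfect criterion for appearance, the text should say that a weak correlation there is not by itself to be read as insensitivity.
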